 - **Hypothesis 3a:** Differences in outcomes between the UP-A and the other two conditions will be mediated by changes in: Distress Tolerance (Using the Behavioral Indicator of Resiliency to Distress; BIRD and Distress Tolerance Scale; DTS) and Behavioral Avoidance (using the Avoidance Hierarchy).
 - **Hypothesis 3b:** Among participants in the TAU+ and UP-A conditions, treatment outcomes will be better for participants whose therapists: 1) rate the YOQ results as more credible, 2) view the YOQ reports more frequently, and 3) discuss the reports with them in session more frequently. Among participants who are flagged as “at risk for treatment failure” by the YOQ, outcomes will be better for those whose therapists report changing treatment strategies in response to the YOQ feedback.
 - **Hypothesis 3c:** Differences in outcomes between TAU and the two treatments using the YOQ (UP-A and TAU+) will be mediated by differences in 1) therapy alliance and 2) therapy engagement.

4) **Background***

Over the last several decades, researchers have developed dozens of disorder-specific evidence-based psychosocial treatments (EBTs) (Chorpita et al., 2011). However, even in the most highly controlled research studies, a substantial percentage of youths with emotional disorders are treatment non-responders (e.g., approximately 40% for anxiety disorders [Walkup et al., 2008], and 52% for depressive disorders [March, Silva, & Vitiello, 2006]). Moreover, the effectiveness of these interventions in community settings has been disappointing. A recent meta-analysis of 52 effectiveness trials of youth psychotherapy concluded that, although EBTs typically outperform TAU, the average effect was small ($d = .29$) (John R. Weisz et al., 2013). In addition, the adoption of EBTs into community practice settings has been slow (McHugh & Barlow, 2012), 2012), suggesting that these treatments still may not be appealing and/or feasible for clinicians and highlighting the need for improved interventions.

A recent innovation in EBTs that may prove more feasible for use in community settings is transdiagnostic treatment. Transdiagnostic approaches draw from theoretical models that explain distinct conditions via common mechanisms and use flexible treatment strategies to address diverse problems simultaneously. Furthermore, this treatment approach may have quicker uptake by CMHC clinicians because: (1) comorbidity is the rule, rather than the exception for patients in

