community. This assessment will include completion of some or all of the questionnaires/procedures listed in the “Pre Treatment” column in Table 2 and described in additional detail below. Randomization will take place following this first assessment once subjects have been deemed eligible for participation. If a participant is unable to begin treatment within 4 weeks of their initial baseline assessment, an abbreviated baseline re-assessment may be conducted prior to the start of treatment. This re-assessment will include review of the symptoms previously endorsed on the ADIS-5-C/P, SCARED, MFQ, YOQ, SDQ, DTS, and Avoidance Hierarchy (see Measures, below).

If any study assessment is to occur at the University of Miami, parents/guardians will be emailed a “paybyphone” link to register their car for parking through the University’s Parking and Transportation department. They may be asked to supply their license plate number so that study staff may register their car for them in the case of user or system error. License plate numbers will be discarded following termination of study participation, and will not be used for research purposes.

At every therapy session, some or all of the assessments/questionnaires listed in the “Every Session” column in Table 2 will be completed. Additional assessments will take place approximately 8 (mid-treatment) and 16 weeks (post-treatment) after treatment initiation, as well as 3 months after the post-treatment assessment. All efforts will be made to have these assessments take place within a specified time window in relation to the 8, 16, or 28 week time-point date. The windows allow for data collection up to two weeks before the time-point date and up to 2 weeks, 4 weeks, or 8 weeks after the time-point date for the mid-treatment, post-treatment, and follow-up evaluations respectively, although data may still be collected should participants miss this window. During these visits, some or all of the measures detailed in the respective assessment point columns in Table 2 will be administered. With the exception of the computer-based tasks (e.g., the BIRD task), all adolescent- and parent-report measures will be available in English and in Spanish. The Spanish translations of these measures will be submitted in an amendment prior to initiating data collection.

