 - **Self-report YOQ Use:** The Session Report Forms (see Session Report Forms under *Assessment of Treatment Differentiation and Fidelity* below) for the UP-A and TAU+ will include items assessing therapists 1) indicating whether they viewed the YOQ report, 2) rating their perception of the credibility of the report on a 7-point Likert-type scale from “Not an Accurate Reflection of My Client’s Progress” (1) to “Extremely Accurate Reflection of My Client’s Progress” (7), 3) indicating whether they discussed the YOQ feedback with their client, and 4) indicating what, if any, changes to the treatment plan they made in response to the feedback .
- **Working Alliance Inventory (WAI):** The short version of the Working Alliance Inventory, completed by the client and therapist, includes 12 items rated on a 7-point Likert-type scale from never (1) to always (7), with items reflecting three core components of alliance: agreement on tasks, agreement on goals, and bond.
- **Engagement in treatment:** Two indicators of treatment engagement will be tracked— 1) Missed sessions will be counted and 2) premature treatment terminations will be documented. Engagement will be tracked throughout the study, although data of interest will be engagement data collected during tracked for the first 16 weeks of treatment only, given potential variability in treatment length across conditions.

Measures to be Completed by Clinicians Only:

- **Therapist Background Questionnaire and Locator Form:** These forms will be used to gather demographic and professional information about clinicians, as well as contact information to help locate the participant for future assessments.
- **Evidence-Based Practice Attitude Scale (EBPAS):** This 15-item rating scale measures provider attitudes toward evidence-based practice and includes four subscales: Requirements, Appeal, Openness, and Divergence.
- **Attitudes Toward Standardized Assessment Scales-Monitoring and Feedback (ASA-MF):** This 18-item rating scale measures provider attitudes toward using standardized progress measures for treatment planning and includes three subscales: Clinical Utility, Benefit for Treatment Planning, and Practicality.
- **Monitoring and Feedback Attitudes Scale (MFA):** This 17-item rating scale assesses provider attitudes toward routine progress monitoring and providing feedback to clients about treatment progress. It has three subscales: Benefit, Harm, and Trust.

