- **TCU Organizational Climate Form (TCU-ORC):** The TCU-ORC is a measure of organizational climate that consists of multiple subscales that can be used based on project needs.
- **UP-A Knowledge Check:** This measure consists of 25 multiple-choice questions covering concepts from Core Modules 1-8 as well as Module-P of the Unified Protocol for the Treatment of Emotional Disorders in Adolescents.
- **UP-C/A Therapist Beliefs Questionnaire:** This is a 22-item measure created for the current study that assesses clinicians' beliefs about the UP-A.
- **Adaptations to Evidence-Based Practices Scale:** Six-item measure about treatment adaptations.
- **Abbreviated Multidimensional Acculturation Scale:** A measure with 42 very brief items that assesses acculturation and cultural identity.
- **Cultural Adaptations Background Survey:** A 6-item measure about clinician's caseload, diversity of clients, and intervention selection and use with clients.

Measures derived from Clinic's Medical Records:

- The following data will be derived from the clinic's medical record for each study participant:
 - **Use of medication**
 - **Treatment attendance**
 - **Session notes**
 - **Supplemental mental health service use**
 - **Funding Source for Services**
 - **Intake and Discharge Diagnoses**
 - **Reasons for Treatment Termination**

Assessment of Treatment Differentiation and Fidelity:

- All clinicians will be asked to complete a Session Report Form after each session. The items included in these forms will vary by condition, but will include reports of who attended the session, how long the session lasted, and items about session content. Clinicians may be asked to include a copy of their session progress note with the form if the project is not able to access session progress notes during the review of clinic medical records.
- All treatment sessions in all conditions will be video or audiotaped; these recordings will be used to monitor ongoing fidelity for UP-A, to quantify treatment adherence in the UP-A and TAU+ conditions, to assure differentiation of treatments, and to document characteristics of TAU.

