Procedures to monitor participant Safety: Throughout the study, the PIs and all study staff will monitor participants' risk of harm, as described above under 9) Study End points. Any evidence of risk of self-harm will be reported immediately to the principal investigators. When possible, at times when patients are seen for the study, a trained mental health professional will be present and available at the clinics to take appropriate measures; at all other times the principal investigators or post-doctoral fellow will help the assessors generate a safety plan. In the case that abuse or neglect is discovered, appropriate measures will be taken, in accordance with the laws of Florida or Connecticut. Prior to making this report, every effort will be made to inform the family first and discuss the situation with them. However, if the family cannot be reached, the report will still be made promptly, as required by Florida or Connecticut statutes. All families will be informed of the limits of confidentiality during the consent process.

If clinical or questionnaire data indicate that a child is showing a notable decline in functioning during the course of the study, this will be discussed with the child's clinician and caregiver and the child will be referred for additional and/or alternative treatment if appropriate.

Procedures to report any Adverse Event or Unanticipated Problem during the study: Throughout the study, the PIs will be responsible for reviewing and reporting adverse events occurring during the study to their local IRB. If any type of adverse event

occurs, the PIs will report that event to the Miami and/or UConn IRB according to the local IRB policies. If an unanticipated problem occurs to compromise the data or confidentiality of the data storage plan (e.g., a break-in to the laboratory space), the PI will notify the IRBs as well as any participant potentially affected by the event.

14) Withdrawal of Subjects*

Participants and their parents/guardians may be withdrawn from the study without their consent if they are withdrawn from clinical care in the CMHC. Should the client be terminated or transferred in accordance with the local clinic policy, he/she will be withdrawn from the study. In addition, participants may be withdrawn for the following reasons:

- Parent/guardian no longer available to participate with the adolescent.
- Failure to adhere to clinic guidelines and/or clinician guidelines.

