- The participant is no longer able to attend clinic visits or complete research assessments.
- There may be other reasons that are unforeseen at this time.
- The clinician and/or evaluator determine, during interim treatment assessments, that an emotional disorder treatment focus is no longer appropriate/sufficient. If this determination is made by the evaluator, the clinician must also agree that emotional disorder focused treatment is no longer appropriate/sufficient and alternative or additional care is necessary.
- During the course of treatment, the adolescent begins an outside psychosocial intervention similar to that given in the study, or one that the investigators feel may be confounding.

Those participants who voluntarily withdraw from treatment may be asked to complete 8 week, 16 week, and 3 month follow-up assessments for data collection purposes, if appropriate.

Clinicians may be excluded from the study for any of the following reasons:

- They leave the clinic and are no longer seeing clients at the CMHC.
- They are unable to attend and/or participate in training and consultation meetings.
- They are determined inappropriate for the research study (i.e. failure to adhere to treatment, failure to adhere to study procedures).

In the event that a clinician is withdrawn or voluntarily withdraws from the study, clients who are still in treatment will be offered to transfer to another study clinician if appropriate. All clinicians will be asked to consider the best interests of the adolescents when withdrawing from the study, and encouraged to complete treatment with study clients before withdrawing.

15) Risks to Subjects*

There are no physical risks associated with participation in the study. There are minor psychological risks to child and caregiver participants. During assessment procedures, there may be some risk of discomfort, irritability, or anxiety resulting from discussion of personal or emotion-provoking subjects. However, this risk is not greater than that which occurs in the usual clinical evaluation process. Participants and their parents/guardians may experience mild inconvenience from having to complete additional research assessments which may take additional time.

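### Section 14 withdraws from the study any adolescent the clinic terminates or transfers and provides later assessment only for voluntary withdrawers, so the primary CGI-I outcome can go uncollected after randomisation

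*Combined protocol and SAP*

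**What the plan says.** Section 14 (Withdrawal of Subjects) of the combined protocol and SAP states: "Should the client be terminated or transferred in accordance with the local clinic policy, he/she will be withdrawn from the study". The sentence before it allows withdrawal without the family's consent when the clinic ends care. Further grounds are listed as discretionary. They include an unavailable guardian, non-adherence to clinic or clinician guidelines, inability to attend or to complete assessments, a judgement that the treatment focus no longer suffices, and outside therapy.

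Assessment after withdrawal appears once: "Those participants who voluntarily withdraw from treatment may be asked to complete 8 week, 16 week, and 3 month follow-up assessments", and then only where appropriate. Separately, if a study clinician leaves, "clients who are still in treatment will be offered to transfer to another study clinician if appropriate".

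The surrounding design is as follows.

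- **Randomisation** follows the baseline assessment and precedes treatment (section 10, Study Procedures).
- **Primary outcome** is a CGI-I of 1 or 2 at 16 weeks and at the 3-month follow-up (section 9). Table 2 schedules CGI-I at those two visits only.
- **Primary analysis** is a logistic multilevel model (section 12, Data Analysis Plan). No analysis population and no rule for a missing CGI-I are given with it.
- **Engagement** (section 10): missed sessions are counted and "premature treatment terminations will be documented". The data of interest are limited to the first 16 weeks, "given potential variability in treatment length across conditions". Under Hypothesis 3c, outcome differences between TAU and the two YOQ arms "will be mediated by differences in 1) therapy alliance and 2) therapy engagement".
- **Clinic records** supply, among other items, "Reasons for Treatment Termination".

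**The concern.** Section 14 ties being in the study to being in clinic care. A clinic closing or moving a case is an event after randomisation and may be related to how the adolescent is doing. Taken as written, the rule removes that adolescent from the study, and the one sentence on continued assessment does not reach the case.

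CGI-I is exposed because it has no early rating. Removal before week 16 without reassessment leaves no primary outcome at all, and removal between week 16 and the follow-up can lose the second one.

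If outcome-dependent loss differs between arms, the odds ratio for the arm comparison is biased, in a direction that cannot be known in advance. If such loss is the same in every arm, the odds ratio is not biased but precision falls. There are reasons to think a difference possible: clinicians know the arm, YOQ alerts exist only in UP-A and TAU+, TAU has no set duration (section 8), and the protocol itself expects treatment length to vary by condition. None of these shows that a difference will occur. An outcome that was never collected cannot be recovered at analysis.

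**Working it through.** **1. Does any other text supply the missing assessments?**

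| Provision | Whom it covers | Reaches clinic-removed adolescents? |
|---|---|---|
| Section 14, assessment after withdrawal | Voluntary withdrawers from treatment | Not as written |
| Section 14, another study clinician | Clients whose clinician leaves the study | No; a different event |
| Section 10, late visits: "although data may still be collected should participants miss this window" | Participants who miss a window | Not extended to those withdrawn |
| Section 21, online, phone or video completion | Participants unable or unwilling to attend | Not extended to those withdrawn |
| Section 10, locator form; section 18, steering-committee review of retention and missing data | The study generally | Could help; neither says so |

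No text forbids assessing these adolescents and none provides for it.

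**2. Limits, with no loss rate assumed.** Inputs: 222 enrolled (section 6), allocation 1:1:1 (section 10, Randomization), so 222/3 = 74 per arm. With k outcomes uncollected in an arm, its response rate is undetermined over k/74. The difference between two arms is undetermined over (k₁ + k₂)/74.

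- One outcome in one arm: 1/74 = 1.4 percentage points of that arm's rate
- One per arm: 2/74 = 2.7 points on the difference
- Four per arm (5.4%): 8/74 = 10.8 points
- Seven per arm (9.5%): 14/74 = 18.9 points

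Section 24 counts differently: 300 enrolled, with 222 completing treatment. On that reading there are 300/3 = 100 per arm and each uncollected outcome is worth 1.0 point. These widths apply to any missing outcome, whatever its cause.

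**3. Illustration on assumed rates.** Nothing in this step comes from the documents except 74 per arm. Assume true response of 60% in UP-A and 40% in TAU (odds ratio 2.25). Let w_r and w_n be the fractions of responders and non-responders lost. Then

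observed OR = true OR × [(1 − w_r,U)/(1 − w_n,U)] / [(1 − w_r,T)/(1 − w_n,T)].

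A 5% loss in every group stands for refusals and untraceable families. All further loss is placed on non-responders, which is itself an assumption.

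| Responders/non-responders lost (%), UP-A vs TAU | Observed OR | Difference (points) |
|---|---|---|
| 5/5 vs 5/5 | 2.25 | 20.0 |
| 5/20 vs 5/20 | 2.25 | not biased on the OR scale |
| 5/10 vs 5/20 | 2.25 × 0.80/0.90 = 2.00 | 61.3 − 44.2 = 17.1 |
| 5/20 vs 5/10 | 2.25 × 0.90/0.80 = 2.53 | 64.0 − 41.3 = 22.7 |

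Further adolescents lost, over two arms: row three, 29.6 × 0.05 + 44.4 × 0.15 = 8.1; row four, 29.6 × 0.15 + 44.4 × 0.05 = 6.7. If half of this further loss is reassessed, the odds ratios become 2.25 × 0.875/0.925 = 2.13 and 2.25 × 0.925/0.875 = 2.38. With a true null at 50% in each arm, the two unequal patterns give odds ratios of 0.89 and 1.13 (−2.9 and +2.9 points).

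The standard error of the log odds ratio is √Σ(1/cell), before clustering. It is 0.344 in row one and 0.360 in row two, 4.6% larger. In row three it is 0.353, so the shift ln(2.25/2.00) = 0.118 is 0.118/0.353 = 0.33 of a standard error.

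**The case against.** The strongest reply is that this is one unclear sentence. If *terminated* covered ordinary discharge, the schedule could not work: visits are timed from treatment initiation, TAU has no fixed length, and a 3-month follow-up is planned (sections 8 and 10). The intended group is therefore narrower than the words. A case the clinic closes after a family stops attending may also count as a voluntary withdrawal. The locator form, the steering committee's review of missing data, and the collection of clinic-record data through follow-up (section 26) suggest a team that means to keep hold of participants. All of this stands as a limit on how many adolescents are affected. It does not supply the missing provision.

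A reader might infer more than the documents support, in five ways.

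- *The plan forbids assessing these adolescents.* It is silent. The consent pages are not in the copy reviewed, so what families are told about contact after withdrawal cannot be judged.
- *Loss will differ by arm, so the result will be biased.* No text links a YOQ alert to termination, and the remark about varying treatment length is not about clinic-initiated removal.
- *The odds-ratio scenarios measure this rule.* They rest wholly on assumed rates. The documents do not say whether removed adolescents are more often responders or non-responders.
- *Hypothesis 3c cannot be tested.* Premature terminations include voluntary dropouts, whom section 14 allows to be assessed, and alliance and missed sessions are mediators too. Only some cases may be affected.
- *The SCARED and MFQ analyses are safe because those measures are also taken at baseline and 8 weeks.* That depends on how baseline enters the model, which the Data Analysis Plan does not state.

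**Conclusion.** The point holds in a limited form. The withdrawal rule is mandatory for clinic termination or transfer, later assessment is written only for voluntary withdrawers, and CGI-I has no rating before week 16. Following the text can therefore lose primary outcomes after randomisation. Whether it does, how often, and in which arm cannot be learned from the documents.

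The firm figure is a limit, not an expected bias: 1.4 percentage points of an arm's response rate per uncollected outcome at 74 per arm. In the assumed unequal-loss example, about eight further losses over two arms move the odds ratio from 2.25 to 2.00, roughly one third of a standard error. This is worth correcting because the remedy is cheap and the loss is irreversible. It does not by itself undermine the trial. Confidence is medium, since practice may be better than the wording.

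**What to change.** - Reword section 14 so that leaving clinic care, or being withdrawn by the clinic or study, does not by itself end outcome assessment.
- Seek the 8-week, 16-week and 3-month follow-up assessments from every randomised adolescent who is able to complete them and whose consent or assent for assessment stands. Use the community locations in section 8 and the remote options in section 21.
- Reconcile *terminated* and *transferred* with the follow-up schedule (sections 8 and 10) and with the offer of another study clinician (section 14).
- Report withdrawals by arm, timing and reason, drawing on the termination reasons already taken from clinic records, and add a sensitivity analysis for CGI-I still missing. The method is the statistician's choice. This part remains possible even if data collection has closed.

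No treatment-stopping or referral rule is proposed.

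The cost is independent-evaluator time for visits that were already planned, some added review load (20% of interviews are re-rated), modest tracking, and amendments at two IRBs, possibly with consent changes. Payments are those already set in section 23: $20 + $80 + $80 = at most $180 per retained family, before BIRD payments. Families who refuse or cannot be traced will still be missing.

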Subject participation: Given the flexibility of the UP-A and TAU interventions, the exact duration of subject participation is estimated to be approximately 25 weeks, plus an additional 3 month follow-up. The UP-A is delivered in 8 to 21 weekly sessions, and no treatment duration is specified for the TAU conditions. 25 weeks is estimated to account for any additional time required for screening and intake (though, as noted above, all efforts will be made to ensure that treatment initiation is not delayed as a result of study participation). However, this interval may vary slightly due to holidays, typical clinic closures or other naturally occurring delays.

Assessments will take place at the CMHC, university setting, Center for Autism and Related Disorders office, and/or in another private setting within the community at baseline, approximately 8 weeks after treatment initiation (estimated to be mid-treatment), and approximately 16 weeks after treatment initiation ([post treatment] estimated to correspond with the length of UP-A treatment, based on average number of sessions from a recent RCT of the UP-A). Finally, a 3 month follow-up assessment will take place 7 months after treatment initiation (16 weeks + 3 months). All efforts will be made to have these assessments take place within a window of +/- 2 weeks when they are scheduled to occur.

Clinician participation: Though efforts will be made to retain the same clinicians throughout the study, we anticipate that there will be personnel turnover at the clinic sites. However, the maximum duration of clinician participation will be approximately four years, as this is the estimated timeline for study completion. UP-A clinicians who stopped participating in the larger study will still be invited to take part in the qualitative interview portion of the study.

Recruitment Timeline: We anticipate that recruitment of all subjects across both sites will take approximately 3.5 years.

Investigator Timeline: We estimate that the primary analyses will be completed at the end of the fourth year of the study once all study assessments have been completed.

Table 1: Study Timeline	Year 1 Months:				Year 2 Months:				Year 3 Months:				Year 4 Months:			
	1-3	4-6	7-9	10-12	1-3	4-6	7-9	10-12	1-3	4-6	7-9	10-12	1-3	4-6	7-9	10-12
Participant Recruitment and Assessment																
Enrolling clinicians	X Ongoing as needed															
Enrolling new adolescent/caregiver participants		X	X	X	X	X	X	X	X	X	X	X	X	X		

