Study assessments		X	X	X	X	X	X	X	X	X	X	X	X	X	X	X
Data Management Activities																
Final Database Ready																M-11
Final Session Recording Collected															M-7	
IE Coding of Tapes for Fidelity & Differentiation	Ongoing for consultation purposes														X	X
Data Analysis																X
Preparation of manuscripts																X

9) **Study Endpoints***

The primary study outcome will be treatment response. Response will be defined as a Clinical Global Impression-Improvement (CGI-I) of 1 or 2 at 16 weeks after treatment initiation and at the 3 month follow-up. Secondary outcomes will include scores on the Children's Global Assessment Scale (CGAS), Screen for Child Anxiety Related Emotional Disorders-Youth and

Parent Reports (SCARED/-P), and the Mood and Feelings Questionnaire-Self & Parent Reports (MFQ), as well as diagnostic status on Anxiety Disorders Interview Schedule for the DSM-5, Child Version, Child and Parent Report Forms (ADIS-5-C/P).

The following measures will be taken to monitor data relating to safety:

Throughout the study, trained study staff will monitor participants' risk of harm. It is possible that participants' clinical data might indicate, for example, that a parent or adolescent is at risk (e.g., adolescent or parent reports suicidal ideation, or an adolescent's physical safety or well-being is in question). In order to address such situations, all study therapists and staff will be thoroughly trained in the ethics of conducting research with human participants, and will be thoroughly educated about the project's data safety and monitoring procedures. All such incidents will be reported immediately to the principal investigators, and, if necessary, to the local IRB according to their policies.

In addition, we will use the short version of the Columbia-Suicide Severity Rating Scale (C-SSRS) at baseline, 16 weeks, and 3 month follow-up and following any evidence of suicidal ideation or significant adolescent deterioration. The C-SSRS allows the IE to gather information on suicidal behavior, suicide attempts, and presence and intensity of suicidal ideation. The information will be used to identify adolescents possessive of active suicidal ideation, intent or plan that may need to be excluded due to needs for more acute care.

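### Section 14 takes youths whom the clinic terminates or transfers out of the study, and secures no later assessment for youths withdrawn by the clinic or study, so their primary CGI-I can be lost

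*Combined protocol and SAP*

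**What the plan says.** Section 14 (Withdrawal of Subjects) ties staying in the study to staying in clinic care.

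- **Mandatory rule.** "Should the client be terminated or transferred in accordance with the local clinic policy, he/she will be withdrawn from the study".
- **Permissive rule just before it.** Participants "may be withdrawn from the study without their consent if they are withdrawn from clinical care in the CMHC".
- **Further permissive grounds.** One is a finding by the clinician, the evaluator or both that an "emotional disorder treatment focus is no longer appropriate/sufficient"; if the evaluator reaches it, the clinician must agree. Another applies if, while treatment is under way, "the adolescent begins an outside psychosocial intervention similar to that given in the study, or one that the investigators feel may be confounding".
- **A protected case.** When a study clinician leaves, "clients who are still in treatment will be offered to transfer to another study clinician if appropriate".
- **Assessment afterwards.** "Those participants who voluntarily withdraw from treatment may be asked to complete 8 week, 16 week, and 3 month follow-up assessments", where this is appropriate. No sentence covers youths withdrawn by the clinic or the study.

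Section 9 defines response as "a Clinical Global Impression-Improvement (CGI-I) of 1 or 2 at 16 weeks after treatment initiation and at the 3 month follow-up". Table 2 in Section 10 schedules the CGI-I at those two visits and not at 8 weeks. The Data Analysis Plan in Section 12 names a logistic multilevel model for response and states no analysis population and no method for missing outcomes.

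**The concern.** Stopping treatment and leaving the study are different events, and Section 14 merges them. Followed as written, a youth whom the clinic terminates or transfers before week 16 need never have a CGI-I. The model has no earlier CGI-I from that youth to draw on. One withdrawn after week 16 keeps the 16-week rating and can lose the follow-up rating.

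The reasons for such withdrawal are plausibly related to outcome. Sections 9, 13 and 15 send youths who decline notably for additional or alternative treatment. Section 14 then allows withdrawal if emotional-disorder treatment is judged insufficient, or if qualifying outside care begins. That route would tend to remove non-responders, but other terminations or transfers, such as administrative ones, need not.

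At stake are the response comparisons in Hypotheses 1 and 2. Equal loss of similar youths from arms with the same response rate creates no false difference. A false difference needs loss, or its relation to outcome, to differ by arm. This could happen: the treating clinician, who knows the arm, takes part in the judgement about treatment focus, and only the two YOQ arms receive alerts about poor progress. The documents do not show that it will.

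**Working it through.** The plan gives no withdrawal rate, planning response rate, power or significance level, so it has no figure of its own to reproduce. What follows is illustrative.

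**Inputs from the documents.** 222 adolescents (Section 6), allocated 1:1:1 (Section 10): 222 / 3 = 74 per arm.

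**Assumed inputs.** True response r = 40% in both compared arms. Share lost without a CGI-I w = 5 to 15%, which is 74 × 0.05 = 3.7 to 74 × 0.15 = 11.1 youths per arm. Response among those lost q = 0 to 60%. Two-sided 5% test.

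**Step 1: observed response in one arm.** Observed = (r − w·q) / (1 − w). For example, w = 0.15 and q = 0 gives 0.40 / 0.85 = 47.1%.

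| w | q = 0 | q = 20% | q = 40% | q = 60% |
|---|---|---|---|---|
| 5% | 42.1% | 41.1% | 40.0% | 38.9% |
| 10% | 44.4% | 42.2% | 40.0% | 37.8% |
| 15% | 47.1% | 43.5% | 40.0% | 36.5% |

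When those lost respond like everyone else (q = 40%), there is no bias at any w.

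**Step 2: unequal loss, same kind of youth lost.** The true difference is zero. A positive value favours the arm that loses more.

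| Loss | q = 0 | q = 20% | q = 40% | q = 60% |
|---|---|---|---|---|
| 10% v 5% | +2.3 | +1.2 | 0 | −1.2 |
| 15% v 5% | +5.0 | +2.5 | 0 | −2.5 |

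**Step 3: equal loss, different youths lost** (q = 20% in one arm, 60% in the other).

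- 5% lost: 41.1% v 38.9%, a difference of 2.1 points.
- 10% lost: 42.2% v 37.8%, a difference of 4.4 points.

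The sign depends on which arm loses which youths.

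**Step 4: size against sampling error.** SE = √[p₁(1−p₁)/n₁ + p₂(1−p₂)/n₂], with n = 74(1 − w) and clinician clustering ignored.

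- 15% v 5%, q = 0: n = 62.9 and 70.3, SE = 8.62 points, ratio 4.95 / 8.62 = 0.57.
- Equal 10% loss: SE = 8.48 points, ratio 0.52.
- Equal 5% loss: SE = 8.26 points, ratio 0.25.

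For the largest case (unrounded ratio 0.575), type I error is P(Z > 1.96 − 0.575) + P(Z < −1.96 − 0.575) = 8.3% + 0.6% = 8.9%, against a nominal 5%.

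**The case against.** The best defence is that the plan does not set out to stop assessing youths when treatment stops. Only the termination or transfer sentence is mandatory; the other grounds are discretionary. Providing for voluntary withdrawals does not forbid assessing others. Section 10 allows data collection outside the visit windows, Section 21 allows remote completion, and premature terminations are tracked as an engagement measure for Hypothesis 3c, which needs outcomes for at least some youths who stop early. All of this is true and makes the gap smaller. None of it says that a youth withdrawn from the study by the clinic or study will still be assessed.

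Three stronger readings are tempting, and the documents do not support them.

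- **Planned discharge counts as termination.** Section 8 says "The UP-A is delivered in 8 to 21 weekly sessions, and no treatment duration is specified for the TAU conditions", so a reader might infer that responders who finish early are dropped, and at arm-specific times. But the same section fixes the 16-week and follow-up visits from treatment initiation, whatever the length of treatment, so many youths must be expected to finish before the last visit. Treatment length should not be used as a mechanism for bias.
- **Any additional care triggers withdrawal.** Section 14 requires either a judgement about treatment focus or a similar or possibly confounding psychosocial intervention begun during treatment. Referral for more care, or care begun after treatment ends, is not itself a ground. The Service Utilization form is scheduled at 16 weeks and follow-up, so some outside service use is expected among youths still being assessed.
- **A quarter of outcomes will be missing.** Section 24 speaks of 150 enrolled per site and 222 completing treatment, which gives 1 − 222/300 = 26%. Section 6 instead treats 300 as the number recruited and screened, and not completing treatment is not the same as lacking a CGI-I.

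The objection that bias is unproven also stands. The YOQ route in particular is speculative, since Section 10 has clinicians use the feedback to adjust treatment, not to withdraw youths.

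**Conclusion.** The point holds as a gap in a stated rule. Section 14 mandates study withdrawal on clinic termination or transfer, permits it on two further treatment-related grounds, and secures no CGI-I afterwards. The loss is plausibly related to response, in an uncertain direction.

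Bias in the arm comparison is possible but not demonstrated. Under the assumptions above it runs from zero to about 5 percentage points either way, or 0.6 standard errors or less. The largest case needs threefold unequal loss and no responders among those lost. Every input except 74 per arm is assumed. The change is still worth making, because a CGI-I not collected at the time cannot be recovered later and the remedy is cheap.

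**What to change.** 1. Amend Section 14 so that clinic termination or transfer, qualifying outside care, or a judgement that more than emotional-disorder treatment is needed ends study treatment at most, not study participation.
2. Extend the sentence on later assessment to all such youths in every arm, and change *may be asked* to *will be asked* for the 16-week and 3-month assessments including the CGI-I, remotely if needed as Section 21 already allows, unless consent or assent is withdrawn.
3. Add one sentence to the Data Analysis Plan: these youths are analysed in the arm to which they were randomised.

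Optional: use one verb, *may* or *will*, in the first two sentences of Section 14, and add a sensitivity analysis for youths who had outside psychosocial care.

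**Cost.** No new visits or measures. Section 23 pays $80 for each of the two visits, so $80 + $80 = $160 per youth, apart from the small BIRD incentive. If 5 to 15% of 222 are affected (11 to 33 youths), that is 11 × $160 = $1,760 to 33 × $160 = $5,280, plus evaluator time.

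**Downside.** Some analysed youths will have had outside care, and one who improves because of it counts as a responder. The Service Utilization form already records such care, so its extent can be described.
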